3.1.2. Recruitment

Aim 1 will involve original data collection, conducted either in-person or remotely. Qualitative and quantitative data will be collected from cancer survivors to inform the development of mindEMI. Survivors who are current smokers will be recruited in 2 ways. First, using electronic medical records at Moffitt, a trigger that is configured in the electronic system will notify our study team weekly of patients who are classified as current smokers, and study staff will contact potential participants. This recruitment strategy has been successfully implemented by co-primary mentor, [name] research team^{66,67} (recruiting 4.6 cancer patients per month, who were interested in quitting but have

not completely quit, similar to the current proposal's sample characteristic).¹² She successfully recruited 7 and 12 cancer patients per month in her $R03^{12}$ and R01,⁶⁸ respectively and recruited one of the largest samples of this population in the literature to date (N = 412). Second, [name] team at the Cancer Survivorship Clinic at Moffitt will connect potentially eligible participants with the study team, and the study team will contact them.

3.2. Aim 2: Usability Testing

3.2.1. Participants and Recruitment

Aim 2 will recruit 10 survivors, independent from Aim 1, to pilot the prototype mindEMI. Recommended sample size in usability studies is at least N=10 to capture 94.7% of potential usability problems, which guided the current sample size,⁶⁹ accounting for 30% drop out with a desired final sample size of 10 (will recruit N=13). Recruitment and eligibility will mimic Aim 1, with the addition of a few eligibility criteria. Additional inclusion criteria: (1) Willing to give quitting a try as part of the study; (2) Having a smartphone that allows installation of the app; and (3) Willingness to download and use the app daily. Additional exclusion criteria: (1) current use of smoking cessation medications (e.g., patch, gum, lozenge, nasal spray, inhaler, or any other nicotine replacement products or medications such as Chantix, Zyban, or Wellbutrin with the intent to quit smoking); (2) evidence of current psychosis; and (3) current/planning pregnancy or lactation. During the phone screen, we will ask participants to consult their physicians before nicotine patch use, if they endorse medical conditions (e.g., recent heart attack, heart disease, angina, high blood pressure not controlled by medications, stomach ulcer, diabetes type 1).⁷⁰

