4.2.2. Aim 2: Procedure and Data Collection

Aim 2 will be conducted remotely. Importantly, the mindEMI content will comprise brief mindfulness strategies and meditations selected and/or modified *per survivors' feedback* from Aim 1 and EMA items will assess *both cancer-specific and general smoking relapse vulnerabilities* by including psychometrically sound items including cancer-specific items.⁸⁸⁻⁹¹ Thus, the prototype will be adapted specifically to survivors.

PI: [name]

Study participation will last 4 weeks, with 2 assessments and 3 brief counseling sessions (Figure 2). Participants will be enrolled in the study once they have completed the baseline survey. Treatment will entail brief cessation counseling over the telephone or Zoom conferencing tool per participants' preferences, provision of written cessation materials (i.e., NCI's Clearing The Air booklet),⁹² and nicotine replacement therapy (NRT) in the form of nicotine patch and its instructions (e.g., suggested areas of body to put on) sent via mail; and brief mindfulness strategies/meditations delivered one-week pre-quit and 2 weeks post-quit. The mailout will also include instructions on how to use the app, and details about the study timeline. Meditations will continue 3 weeks post-quit.

Following the phone screen, eligible individuals will provide verbal informed consent and will be scheduled for the 1st counseling session. Baseline measures will be sent via REDCap to be completed online prior to the 1st session, during which participants will be oriented to the app for mindEMI and EMAs. The quit date (QD) will be scheduled for within about one week after the 1st session.

-14 (QD-2W) +21 (QD+3W) +84 (QD+12W) Day -7 (QD-1W) +14 (QD+2W) +/ (QD+1W) (QD) Intervention MBI delivered via Smartphone app Nicotine Replacement Therapy 2nd Brief Counsel 3rd Brief Counsel 1st Brief Counsel Assessment Baseline End of Tx FollowUp Ax [ROO phase only **Ecological Momentary Assessment** Figure 2. Study 2b Participant Flow of mindEMI (Note. QD = Quit Date, W = Week, Ax = Assessment, Tx = Treatment)

The 2nd session will occur around the QD and the 3rd session will take place approximately at the end of treatment (i.e., mindEMI; QD+2W).

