4.2.5. Aim 2: Adverse Reactions

Minimal risks are anticipated for this study. Data including self-report and interview (psychological and medical) involve risk of breaches in confidentiality. Participants will always be given the option to refuse to answer any questions on the measures that may be distressing. For Aim 2, data will also be collected via smartphone. As such, there are always risks associated with privacy when collecting data in this format.

Successful abstinence may cause irritability, anxiety, general distress, and difficulty concentrating. The nicotine patch that participants will wear beginning on the guit date in Aim 2 will be the

appropriate dose for their level of smoking, and the patch should aid in the management of withdrawal symptoms. The nicotine patch and smoking cessation counseling have been shown to be safe and effective for smokers attempting to quit (e.g., the patch is available over-the-counter). However, side effects to the patch may occur and include skin irritation/ rash, nausea, dizziness, dry mouth, diarrhea, nervousness, headache, vivid dreams or sleep disturbances, irritability, and irregular heartbeat.

Risks will be protected against as described below. This study involves no investigational drugs or devices.

Emergency procedures will be in place should any psychiatric emergency arise during the screening and/or treatment processes. Although this is likely to be very rare, all study personnel will be trained in these procedures.

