Potential side effects from the nicotine patch (Aim 2) will be monitored by study staff and the PI. Participants will be told of potential allergic reactions and side effects in response to the patch and nicotine side effects, and also told that they are free to remove the patch at any point in time. Should participants experience side effects, they will be advised to discontinue the patch, and also told to contact the PI and study staff. Given three phone counseling calls will be scheduled with participants, and that discussion of the patch will be conducted at these times, we do not anticipate any issues with monitoring patch side effects. Additionally, initial eligibility screening will exclude those with medical conditions that are contraindicated for the patch. Research staff will report any potential AEs immediately to the PI. The PI will report AEs to the IRB within five business days using the required reporting format. Any SAEs (using the FDA definition of SAEs) will be reported within two days to the IRB and NIH using the required reporting format. Given the relatively minimal risk nature of the proposed research, this is considered a highly remote possibility. Any IRB actions in relation to this protocol will also be reported to NIH.

					Ye	ar 1 (Mon	th)					Year 2 (Month)												
Activity	1	2	3	4	5	6	7	8	9	10	11	12	1	2	3	4	5	6	7	8	9	10	11	12	
Prepare interview materials, measures, and protocol for Aim 1	х	x	x																						
Aim 1: Recruit participants (N=10) Aim 1: Data collection				x x	x x	8	x x	-	x x	x x															
Develop prototype smartphone app for mindEMI Staff testing the mindEMI										х	x x	x x													
Aim 2: Recruit participants (N=10) Aim 2: Data collection													x x	x x	x x	x x	x x	x x							
Finalize the full version of mindEMI																			х	х	х	х	х	х	

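### Aim 2 asks participants with heart disease and similar conditions to see a physician before using the patch, but nothing confirms that they did, and the exclusion claimed in Section 4.2.5 is missing from the eligibility list

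*Combined protocol and SAP*

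**What the plan says.** Aim 2 supplies nicotine patches by mail (Section 4.2.2). Three parts of the combined protocol and SAP deal with who may use them.

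- **Section 3.2.1 (eligibility).** The additional exclusions begin "Additional exclusion criteria: (1) current use of smoking cessation medications" and continue "2) evidence of current psychosis; and (3) current/planning pregnancy or lactation". Aim 2 also takes over the single Aim 1 exclusion in Section 3.1.1, enrolment in a smoking cessation program. Medical conditions are handled separately: "we will ask participants to consult their physicians before nicotine patch use, if they endorse medical conditions". The examples given are "recent heart attack, heart disease, angina, high blood pressure not controlled by medications, stomach ulcer, diabetes type 1".
- **Section 4.2.2 (procedure).** The sequence is phone screen, verbal consent, baseline survey, 1st counseling session, quit date. "The quit date (QD) will be scheduled for within about one week after the 1st session". The date of the patch mailing relative to the 1st session is not given.
- **Section 4.2.5 (adverse reactions).** The start of patch use is fixed by the words "The nicotine patch that participants will wear beginning on the guit date in Aim 2". As a safeguard the section states that "initial eligibility screening will exclude those with medical conditions that are contraindicated for the patch". It also notes that there will be three counseling calls and that "discussion of the patch will be conducted at these times, we do not anticipate any issues with monitoring patch side effects".

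**The concern.** The protocol singles out a group for whom it wants medical advice before patch use, and it lists irregular heartbeat among the patch side effects. For that group the safeguard is one request made at the phone screen. If the participant does not act on it, no later step in the plan would detect this before the quit date.

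The second safeguard, exclusion at screening, cannot be applied as written. A screener working from Section 3.2.1 would enrol a person with a recent heart attack and advise a consultation. One working from Section 4.2.5 might exclude the same person. Section 4.2.5 does not say which conditions it means, so neither screener can be shown to be wrong.

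What is at stake is participant safety and the study's ability to document that its own precaution was followed. The primary outcomes in Section 7.2 (feedback, perceived utility and likability, retention) are not at stake.

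**Working it through.** The plan gives no figure on this point to reproduce, so the main check is a comparison of sections.

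**1. Does the eligibility list contain the exclusion that Section 4.2.5 relies on?**

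| Source | Exclusion criterion | Covers a condition in the consult list? |
|---|---|---|
| 3.1.1 (carried over) | Enrolled in a cessation program | No |
| 3.2.1 (1) | Current cessation medication | No |
| 3.2.1 (2) | Current psychosis | No |
| 3.2.1 (3) | Pregnancy (current or planned) or lactation | No |

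That is 1 + 3 = 4 criteria, and 0 of the 6 named conditions appear among them. Pregnancy and lactation may be partly a patch-related exclusion, but no cardiac, blood pressure, ulcer or diabetes criterion is listed.

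**2. Is the consultation confirmed anywhere before the patch starts?**

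- Phone screen (3.2.1): the request is made. No follow-up is stated.
- Mailing (4.2.2): no condition is attached to sending the patch.
- 1st session (4.2.2, 4.2.5): it comes before the quit date and includes a discussion of the patch. The stated use of that discussion is side-effect monitoring, and it is not said to cover the consultation.
- Quit date (4.2.5): the patch starts. No condition is attached.
- EMA and end of treatment (4.2.3): patch use is recorded. The consultation is not.

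The data would therefore show who used the patch, but not whether a flagged user had spoken to a physician. The time available to consult runs from the phone screen to the quit date, so it is longer than the roughly one week between the 1st session and the quit date.

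**3. How many people might be flagged?**

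The number recruited is 13 (3.2.1, 7.1). The share *p* who would endorse a listed condition is not given; 10% to 40% is an assumption.

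- Expected number flagged = 13 × *p*: 13 × 0.10 = 1.3; 13 × 0.40 = 5.2.
- Chance of at least one = 1 − (1 − *p*)^13: 1 − 0.9^13 = 0.746; 1 − 0.6^13 = 0.999.

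These figures count people flagged, not people harmed or exposed to the gap. The expected number exposed is 13 × *p* × *m*, where *m* is the proportion of flagged people who are not excluded, do not consult, and still start the patch. The documents give no basis for *m*, so the figures above are upper values.

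**The case against.** The strongest reply is that the two sections describe two tiers: contraindicated conditions are excluded, and conditions calling for caution lead to a consultation. On that reading the count of 0 of 6 shows no contradiction, because Section 4.2.5 never says that the six are the contraindicated ones. This is fair as far as it goes. The documents do not show which conditions are meant, and the mismatch is best described as an exclusion without a matching criterion. But the two-tier reading still leaves the first tier empty of any medical condition of this kind and the second tier unverified.

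A second reply is that a participant who starts without consulting has departed from the instruction, so the plan does not itself permit it. That also stands, and it narrows the point to one of verification: the plan gives the instruction and has no means of learning whether it was followed.

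Third, other safeguards exist. The patch is available over the counter and dosed to smoking level, participants may remove it at any time, side effects are monitored, and adverse events are reported to set timelines. Recruitment through the center's records and survivorship clinic suggests that participants have clinical contact. Side-effect monitoring, removal and reporting act only after exposure. The rest does not replace the advice that the protocol itself asks for.

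Fourth, phone-screen and counseling scripts may hold the missing question and are not in the public file. This cannot be ruled out. The protocol should still state the rule that releases the patch.

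Finally, the prevalence range has no source in the documents, and being flagged is not the same as being exposed. Both are true, and the conclusion does not depend on the range.

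**Conclusion.** The concern holds. The plan asks for a medical consultation before patch use, has no stated step to confirm it, and relies on an exclusion that its eligibility list does not contain. Under the 10% to 40% assumption, about 1 to 5 of 13 recruits would be flagged, with a chance of at least one between about 75% and over 99%. Any exclusion under Section 4.2.5, and any consultation that does take place, lowers the number affected. The gap in the text does not depend on these figures.

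This should be corrected. It is a gap in one participant safeguard in a small pilot, and it does not show that the study is unsafe overall or that its primary outcomes are compromised.

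**What to change.** 1. In Section 3.2.1, list the medical conditions that exclude a person from Aim 2, so that the list matches Section 4.2.5. Which conditions belong there is for the sponsor's clinicians to decide.
2. For every other participant who endorsed a listed condition, ask at the 1st session, before the quit date, whether the consultation took place and what was advised. Log the answer.
3. Send that participant's patches only once they report a completed consultation with no advice against the patch. An answer of not yet, or of advice against use, does not release them. The participant continues with the app and counseling without the patch, and can still contribute to the primary outcomes.

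The cost is one scripted question in a discussion already planned, one log field, an edit to the exclusion list, and a separate patch mailing for flagged participants, because the mailout in Section 4.2.2 also carries the app instructions. The real downside is timing. With the quit date about a week after the 1st session, some flagged participants may get the patch late or not at all and would attempt to quit without it. Asking at the 1st session still leaves them the whole interval since the phone screen in which to consult. The step rests on self-report, so it catches a missed or negative consultation that the participant reports, but not one that is concealed.

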3.3. Inclusion of Women and Minorities

Both men and women and members of all races and ethnic groups are eligible for this trial.

4. STUDY DESIGN AND METHODS

4.1. Aim 1

4.1.1. Aim 1: Design

Qualitative data will be collected to inform the development of the mindEMI among survivors, followed by configuring the smartphone app with key MBI practices.

4.1.2. Aim 1: Procedure and Data Collection

Survivors (N=15) will complete a single individual in-depth qualitative interview with a brief survey which will last about 1 hour. The thematic analysis literature recommends the sample size of 6 to 16.71,72 Thus, we will recruit 15-20 participants for analyses. The proposed procedures are based on recommendations in the literature and [name] prior qualitative work.^{72,73} Following the phone screen, eligible participants will provide verbal informed consent and will be scheduled for the phone, zoom, or in-person interview per participant's preference. During the interview, the following topics will be addressed: (1) Several key formal mindfulness meditations (e.g., breathing) of various lengths (5-15 minutes) adopted from Mindfulness-Based Cancer Recovery,74 Mindfulness-Based Relapse Prevention,⁷⁵ and [name] studies⁷⁶⁻⁷⁸ will be briefly introduced. Participants will be guided through 1 to 2 meditations, before giving feedback. Participants' perceived utility and acceptability of the meditations will be assessed via a brief scale developed for Time2Quit⁷⁷ (benchmark: ≥75% reporting useful).⁷⁹ (2) Brief mindfulness strategies (content areas: fear of cancer recurrence, pain, fatigue, and self-compassion; each takes 1 to 3 minutes to complete) will be presented. Participants will practice several strategies, after which overall feedback and comprehensibility of the strategy will be obtained. (3) The mHealth component will be introduced. Preferred frequency and timing of the practice and delivery of MBIs, means of delivery (prompted vs user-initiated), and inclusion of MBIs addressing

cancer-relevant distress will be assessed. (4) Given the perceived need and importance of human support in the mHealth smoking cessation literature,⁸⁰⁻⁸² feedback on preferences for counseling, including modality (in-person vs phone), and timing will be obtained. Participants will be compensated \$20 for completing the interview. Participants can also receive a bonus of \$5 for each online survey completed within 24 hours of being sent the link. Interviews will be audio-recorded and transcribed for content analysis. Using an inductive thematic saturation approach,⁷¹ interviews will continue until saturation is met, when no more new information (i.e., the number of new themes) is obtained. Following the interviews, the prototype of mindEMI will be fully developed and pilot tested in an independent sample of survivors who currently smoke.

4.1.3. Aim 1: Measures

Participants' demographics and perceived utility and acceptability of the meditations and mindfulness strategies will be assessed via a brief scale developed for [name] prior study on a 6-point Likert scale.⁷⁷ (benchmark: ≥75% reporting useful).⁷⁹ Semi-structured interview will ask for the participants' feedback and suggestions on the planned intervention (See the interview guide for specific questions).

In a brief survey, we will use both an established questionnaire as well as questions adapted from previous studies. Participants will complete a survey of demographics (e.g., ethnicity, race, sex, sexual orientation, gender identity, marital status, education, employment status, income), smoking history as assessed by Cancer Patient Tobacco Use Questionnaire (C-TUQ),⁸³ nicotine dependence using Heaviness of Smoking Index,⁸⁴ The Contemplation Ladder,⁸⁵ previous experience with contemplative practice and perceived usability of mindfulness as assessed by the items developed for [name] study,⁸⁶ and perceived usability scale of the Technology Acceptance Model measure.⁸⁷

Additionally, clinical characteristics (e.g., cancer type, date diagnosed with recent cancer) will be assessed by chart abstraction.

4.1.4. Aim 1: Intervention

NA

4.1.5. Aim 1: Adverse Reactions

Minimal risks are anticipated for this study. Research staff will report any potential AEs immediately to the PI. The PI will report AEs to the IRB within five business days using the required reporting format. Any SAEs (using the FDA definition of SAEs) will be reported within two days to the IRB and NIH using the required reporting format. Given the relatively minimal risk nature of the proposed research, this is considered a highly remote possibility. Any IRB actions in relation to this protocol will also be reported to NIH.

4.2. Aim 2.

4.2.1. Aim 2: Design

Pilot the prototype of the mindEMI in an independent sample of survivors and obtain feedback to inform the final version of the mindEMI.

4.2.2. Aim 2: Procedure and Data Collection

Aim 2 will be conducted remotely. Importantly, the mindEMI content will comprise brief mindfulness strategies and meditations selected and/or modified *per survivors' feedback* from Aim 1 and EMA items will assess *both cancer-specific and general smoking relapse vulnerabilities* by including psychometrically sound items including cancer-specific items.⁸⁸⁻⁹¹ Thus, the prototype will be adapted specifically to survivors.

PI: [name]

Study participation will last 4 weeks, with 2 assessments and 3 brief counseling sessions (Figure 2). Participants will be enrolled in the study once they have completed the baseline survey. Treatment will entail brief cessation counseling over the telephone or Zoom conferencing tool per participants' preferences, provision of written cessation materials (i.e., NCI's Clearing The Air booklet),⁹² and nicotine replacement therapy (NRT) in the form of nicotine patch and its instructions (e.g., suggested areas of body to put on) sent via mail; and brief mindfulness strategies/meditations delivered one-week pre-quit and 2 weeks post-quit. The mailout will also include instructions on how to use the app, and details about the study timeline. Meditations will continue 3 weeks post-quit.

Following the phone screen, eligible individuals will provide verbal informed consent and will be scheduled for the 1st counseling session. Baseline measures will be sent via REDCap to be completed online prior to the 1st session, during which participants will be oriented to the app for mindEMI and EMAs. The quit date (QD) will be scheduled for within about one week after the 1st session.

-14 (QD-2W) +21 (QD+3W) +84 (QD+12W) Day -7 (QD-1W) +14 (QD+2W) +/ (QD+1W) (QD) Intervention MBI delivered via Smartphone app Nicotine Replacement Therapy 2nd Brief Counsel 3rd Brief Counsel 1st Brief Counsel Assessment Baseline End of Tx FollowUp Ax [ROO phase only **Ecological Momentary Assessment** Figure 2. Study 2b Participant Flow of mindEMI (Note. QD = Quit Date, W = Week, Ax = Assessment, Tx = Treatment)

The 2nd session will occur around the QD and the 3rd session will take place approximately at the end of treatment (i.e., mindEMI; QD+2W).

mindEMI; QD+2W). During the week following the 3rd session (QD+3W), the end of treatment measures will be sent via REDCap and a brief phone interview will be conducted to collect feedback on mindEMI. Interviews will be audio-recorded and transcribed for content analysis. Smoking status will be measured using 7-day point prevalence of abstinence ([PPA]; no self-reported smoking in prior 7 days). The counseling sessions will be scheduled at/around the appointment that coincides with our timeline, remaining flexible if there may be medically related changes in schedules (e.g., unanticipated complications) or unanticipated conflicts. EMAs will be completed over 4 weeks. Participants will be compensated \$30 and \$60 for completion of baseline and end of treatment assessments (including a brief phone interview), respectively. Those who complete a brief phone interview at the end of treatment will be compensated an additional \$30. Participants can also receive bonus compensation for each online survey completed within 24 hours of being sent the link (\$5 at both baseline and the end of treatment).

Concerted efforts to keep retention high will include phone calls if incomplete EMAs are observed for more than 2 consecutive days, obtaining a functioning phone number, home address, and the name and phone number of 2 collaterals who can provide contact information if the participant is unreachable, and providing compensation for completing assessments, including increased compensation during later study periods.

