4.2.3. Aim 2: Measures

Baseline and end of treatment. At baseline and end of treatment, the self-reported following will be measured: Demographics (baseline only), smartphone-related information (e.g., operating system), smoking history/status,^{83,93} nicotine dependence using 2-item Heaviness of Smoking Index,^{84,94} smoking-related cognitive and affective processes (e.g., withdrawal symptoms),^{85,95-97} team developed measure of previous experience with contemplative practice developed for [name] study (used in Aim 1),⁸⁶ mindfulness using Avoidance and Inflexibility Scale,⁹⁸ Five Facet Mindfulness Questionnaires,⁹⁹ Self-Compassion Scale,¹⁰¹ affect using Positive and Negative Affect Schedule,¹⁰² depression using Patient Health Questionnaire, anxiety using Generalized Anxiety Disorder-7,¹⁰⁵ and cancer-relevant variables including pain, fatigue, and fear of cancer recurrence.¹⁰⁶⁻¹⁰⁸ Chart abstracted cancer variables (e.g., cancer type) will allow us to describe the heterogeneity in our sample. At the end of treatment, additional items will be assessed: smoking status, nicotine patch

PI: [name] use, changes in smartphone and/or carrier, perceived utility and acceptability of the mindEMI using team-developed items that were used in our team's previous studies (e.g., "How helpful were the mindful skills?")^{86,109-111} as well as validated measures.^{87,112-114} During the end of treatment interview,

open-ended questions on the mindEMI and feedback on the app and format of counseling (e.g., number of treatment sessions) will be assessed using the team developed items (e.g., "What did you like about using the app?").

[figure not shown]
App data. EMA measures will consist of self-reported items on state mindfulness using 3 items selected from extant validated measures,¹¹⁵⁻¹¹⁷ 6 affect items,^{102,118} 1 craving item ("I have an urge to smoke"), using a multiple-point Likert scale, and the number of cigarettes smoked and nicotine patch use (yes/no) as well as psychometrically sound cancer-specific items that include: 1 fatigue item (on a 11-point Likert scale),¹⁰⁷ 1 pain item (on a 11-point Likert scale),¹⁰⁶ and 1 item on fear of cancer recurrence (on a 4-point Likert scale).^{91,108,119,120} The EMAs can be completed in <2 minutes.

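### Aim 2 schedules its primary utility ratings and feedback only at end of treatment and plans no feedback or reason for stopping from participants who stop early

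*Combined protocol and SAP*

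**What the plan says.** Section 7.2 names three primary outcomes for Aim 2: open-ended feedback, ratings of utility and likability judged against the Aim 1 benchmark (at least 75% finding it useful, sections 4.1.2 and 4.1.3), and retention of at least 75% to end of treatment. The analysis is descriptive (M, SD, %). No denominator and no handling of missing ratings is given.

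Section 4.2.2 has two assessments, baseline and end of treatment. The second is timed "During the week following the 3rd session (QD+3W", when "the end of treatment measures will be sent via REDCap and a brief phone interview will be conducted to collect feedback on mindEMI". Section 4.2.3 agrees: "At the end of treatment, additional items will be assessed", among them "perceived utility and acceptability of the mindEMI using team-developed items". It places the open-ended questions in the end-of-treatment interview.

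On the start of follow-up, section 4.2.2 says: "Participants will be enrolled in the study once they have completed the baseline survey". The app is introduced at the 1st session, and "The quit date (QD) will be scheduled for within about one week after the 1st session".

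Several contacts fall in between. Session 2 is around the quit date (QD) and session 3 at about QD+2W. Section 4.2.2 adds: "Concerted efforts to keep retention high will include phone calls if incomplete EMAs are observed for more than 2 consecutive days". It also collects two collaterals "who can provide contact information if the participant is unreachable". In section 4.2.4, a short follow-up EMA after each high-risk prompted strategy includes a helpfulness item.

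Section 7.1 recruits 13 to finish with 10, assuming 30% dropout. It justifies the 10 by the share of usability problems (94.7%) that such a sample should reveal.

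**The concern.** The pilot exists to find what is wrong with the prototype before the final version is built. A problem bad enough to make someone give up the app is among the most useful things it could learn. As scheduled, that person is first asked for formal ratings and feedback at end of treatment, and no item anywhere records why they stopped.

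Two results could be affected. The useful percentage may come from a group in which early leavers are under-represented. The list of usability problems may lack their problems, or hold them as late recollections. Section 1 links the feasibility and acceptability benchmarks to a future R01 trial, and the activity timeline goes directly from Aim 2 data collection to finalizing the intervention. A reason for stopping that was not asked for in time would be hard to obtain later.

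**Working it through.** **The plan's own figure.** Section 7.1: final sample 10, dropout 30%, recruit 13. This is reproduced by 10 × 1.30 = 13. If 10 of 13 finish, 3 people may have no rating or interview. At exactly 30% dropout, 13 × 0.70 = 9.1 finish, so about 3 to 4 may have none.

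**What each contact collects.**

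| Contact | Stated purpose | Feedback or reason for stopping? |
|---|---|---|
| Missed-EMA call (4.2.2) | Retention | None assigned |
| Collaterals (4.2.2) | Tracing | None assigned |
| Counseling sessions 2 and 3 (4.2.2) | Treatment | None assigned |
| Helpfulness item (4.2.4) | Follow-up after high-risk prompts | Momentary only; not named as the benchmark measure |
| End-of-treatment survey and interview (4.2.2, 4.2.3) | Outcome assessment | Yes, all of it |

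**Delay for someone who stops before the quit date.** App use starts at about QD-1W. The formal items come between QD+2W and QD+3W.
- Stop at QD-1W: 1 + 2 = 3 weeks to 1 + 3 = 4 weeks.
- Stop at QD: 2 to 3 weeks.
- Overall: about 2 to 4 weeks. This applies to the formal items, not to all contact.

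**Bounds on the useful percentage.** Let u be the number of responders saying useful, r the responders and n the enrolled. Among responders the result is u/r. Over all enrolled it lies between u/n (every missing person not useful) and (u + n − r)/n (every missing person useful). The ratings are assumed, since the documents give none. Some recruits may be lost before the baseline survey and so never be enrolled, so n is varied.

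| u/r | n | Lower | Upper |
|---|---|---|---|
| 8/10 = 80% | 13 | 8/13 = 62% | 11/13 = 85% |
| 8/10 = 80% | 12 | 8/12 = 67% | 10/12 = 83% |
| 8/10 = 80% | 11 | 8/11 = 73% | 9/11 = 82% |
| 9/10 = 90% | 13 | 9/13 = 69% | 12/13 = 92% |
| 10/10 = 100% | 13 | 10/13 = 77% | 13/13 = 100% |

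The 8/10 and 9/10 rows fall on both sides of 75%; the 10/10 row does not. With 13 enrolled, 0.75 × 13 = 9.75, so 10 people must say useful. Starting from 8 of 10, two of the three missing people would have to agree (10/13 = 77%); if only one did, the figure is 9/13 = 69%.

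**What reaching leavers buys.** Each missing person leaves 1/13 = 7.7 percentage points open. Three missing leave 3/13 = 23 points. Reaching two of the three leaves 8 points.

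**The case against.** The plan does not lose sight of people who stop. Someone who stops in the first week is due a call once EMAs have been incomplete for more than two consecutive days, and a counseling session around the quit date. Collaterals help to trace those who cannot be reached. Nothing makes the end-of-treatment survey or interview conditional on app use, and payment favors that visit: $60, plus $30 for the interview and a $5 bonus, against $30 plus $5 at baseline. Retention is itself a primary outcome, so readers will see how many did not finish. The helpfulness items give some data from later leavers. The study is a small descriptive pilot, and section 1 states no go/no-go rule.

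Most of this stands, and it rules out three stronger readings. A reader might infer that no contact is planned when someone stops; sections 4.2.2 and 4.2.4 show otherwise. A reader might infer that leavers are shut out, so that the results rest mainly on those who stayed. That would require app leavers also to be non-responders at end of treatment, which the documents do not establish. A reader might infer that the useful percentage will be too high, but no ratings from leavers are given, so the direction is a risk and not a finding.

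What remains is that none of the interim contacts is given a feedback question or a reason for stopping. The retention figure shows how many left, not why or what they thought. The helpfulness item ends with app use and follows only high-risk prompts.

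**Conclusion.** The concern holds in a limited form and is minor. The formal utility items and feedback are collected once, at end of treatment. Neither feedback nor a reason for stopping is planned at discontinuation, and the 75% utility benchmark has no stated denominator. The views of people who stop may be under-represented, or recorded about 2 to 4 weeks late if they stop before the quit date.

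The 62% to 85% range rests on three assumptions: 8 of 10 responders say useful, all 13 recruits are enrolled, and three give no rating. It narrows if fewer were enrolled or more respond, and it clears 75% entirely if all 10 responders say useful. It shows how much is left open; it does not estimate bias.

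**What to change.** 1. **Section 4.2.2.** When a participant says on a missed-EMA call or at a counseling session that they have stopped using the app or are withdrawing, ask the reason and offer the brief utility items and feedback questions then. Do not do this for people who have only missed EMAs and are continuing. Still send the end-of-treatment link. State that the end-of-treatment rating counts toward the benchmark if given, and that otherwise the exit rating is used and reported as such.

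2. **Section 7.2.** Report the useful percentage among responders with its count. Beside it, give a labelled worst-case sensitivity line over everyone enrolled (baseline survey completed), with missing counted as not useful. The benchmark is unchanged.

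The cost is a few minutes on contacts already planned, a short addition to 4.2.2 and one descriptive line in 7.2. The published figure may look less favorable, and people who cannot be reached will still be missing.
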